5.4.2 Association between longitudinal measures of TGF β 1 and late gastrointestinal toxicity

We will examine whether levels of TGF β 1 measured in urine and plasma at various timepoints during and after therapy are associated with late gastrointestinal toxicity. Of particular interest will be examining whether changes in TGF β 1 measured over time affect the probability of RTOG ≥ 2 toxicity at 12 months after the completion of radiation therapy. The analysis will be done by relating change in TGF β 1, evaluated by estimating a slope using least-squares regression on each patients repeated follow-up measurements, and the probability of RTOG ≥ 2 at 12 months after completion of therapy using logistic regression. These analyses will be done with and without adjustment for radiation dose to non-target organs (radiation dosimetry). Interest will focus on whether a positive change in TGF β 1 over time (positive slope) is associated with an RTOG ≥ 2 toxicity at 12 months post-therapy. We expect that, on average, approximately 60% of patients will have a RTOG ≥ 2 at 12 months. We also assume that at a minimum of 76 patients of 120 accrued to the study will be alive at 12 months (there is a 95% chance that there will be 76 or more patients will be alive and evaluable at 12 months if the one-year survival/evaluable rate is 70%). Assuming a that 76 patients will be evaluated for toxicity at 12 months and that 50% of estimated slopes are positive, we will have 93% power to detect a difference in the proportion of RTOG ≥ 2 at 12 months of 80% for a positive slope as compared with 40% for a negative or zero slope with a Chi-square test at the 0.05 significance level. A logistic regression analysis treating the estimated slope as a continuous variable should have more power than the Chi-square test.

5.4.3

Analysis of secondary objectives

We will compare the accuracy of DNA mutations and DNA methylation tests in serum, urine, and stool (relative to tumor biopsy) by comparing estimated sensitivities and specificities of the various tests.

We will evaluate which biological fluid provides the best source of tumor specific DNA for association with subsequent disease using logistic regression and Cox proportional hazards models with DNA tests from the different fluids being independent variables in the models.

We will relate novel serum, urine, and stool markers measured during and shortly after treatment to toxicity using logistic regression analysis similar to 5.3.2.

We will examine the relationship between radiation dose and serum, urine, and stool biomarkers measured longitudinal during and after treatment using linear mixed models.

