1.0 INTRODUCTION

1.1 STUDY OBJECTIVES

1.1.1 Primary Objectives:

- To determine if tumor specific DNA mutations and aberrant DNA methylation found in the tumor of patients treated with definitive intent for gastrointestinal malignancies can be detected in the serum, urine, or stool at the time of diagnosis
- To determine if changes in mutational status at follow-up are associated with disease persistence, recurrence, or survival.
- To determine if pre-treatment, post-treatment, and follow-up measurements of TGF β 1 in the urine and plasma can be used to predict late gastrointestinal toxicity.

1.1.2 Secondary Objectives:

- To determine which biological fluid (serum, urine, or stool) is most highly associated with the detection of tumor specific DNA mutations and tumor specific DNA methylation.
- To determine which biological fluid (serum, urine, or stool) provides the best source of tumor specific DNA to measure at follow-up for association with disease persistence, recurrence, or survival.
- To determine if novel serum, urine, and stool biomarkers obtained at the time of treatment and shortly after treatment can be used to predict the likelihood of chronic gastrointestinal toxicity in patients receiving radiotherapy for gastrointestinal malignancies.
- To determine whether novel serum, urine, and stool markers obtained at the time of treatment and shortly after treatment are influenced by the radiation dose delivered to abdominal organs.

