3.2.1.2.2 Collection Schedule

Pre- treatment, pre-radiotherapy (if different than pre-treatment) at completion of radiotherapy and in follow- up at 1, 3, 6, 12, 24, and 36 months

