3.3 ON STUDY EVALUATION

3.3.1 Pre-Treatment (baseline)

- Informed consent obtained
- Clinical evaluation

See 2.2.1

Baseline acute RTOG toxicity assessment (appendix IIIA)

- Laboratory Evaluation

See 2.2.2

Hepatitis B

Hepatitis C

CBC, ALT, AST, total bilirubin, serum BUN, serum creatinine

- Research Specimen Collection:

- Blood, urine, stool (see 3.2.1.2)
 - baseline intestinal permeability test, 6 hour urine (see 3.2.2)

- Pathologic confirmation and biopsy of tumor tissue (see 2.2.3)

3.3.2 *Radiation Treatment Phase*

- Patients will receive radiotherapy for carcinoma of the esophagus, stomach, pancreas, bile ducts, or rectum on an NCI protocol
- At completion of radiation (within the final five fractions)
 - Research Specimen Collection:
 - Blood, urine, stool (see 3.2.1.2)
 - Toxicity Evaluation: RTOG - Acute Radiation Morbidity Scoring Criteria (Appendix IIIA)

3.3.3 *Post Active Treatment Evaluation (follow- up)*

- 3.3.3.1 Patients will be seen for routine follow-up at 1, 3, 6 and 12, 24, and 36 months post-radiotherapy.

- 3.3.3.2 These follow- up visits will include:

- Clinical Evaluation
 - A complete history and physical exam detailing the patient's disease status, bowel function, and medication requirements related to gastrointestinal toxicity. All post-radiotherapy adjuvant therapy will be recorded.
 - Toxicity Evaluation: Complete RTOG - Radiation Morbidity Scoring Criteria (Appendix IIIA, acute at 1 month and IIIB, late at 3, 6, and 12, 24, and 36 months follow-up.
- Laboratory Evaluation
 - As clinically indicated. The presence of accepted serum tumor markers (ie CA 19-9) in excess of defined maximum ranges will be recorded as evidence of disease recurrence.
 - CBC, ALT, AST, total bilirubin, serum BUN, serum creatinine
- Research Specimen Collection:
 - Blood, urine, stool (see 3.2.1)
 - intestinal permeability test, 6 hour urine (see 3.2.2) AT ONE AND THREE MONTHS ONLY
- Radiologic Evaluation
 - As clinically indicated by primary site and primary protocol. For the purpose of radiographically evaluating disease status to correlate to laboratory findings the following radiographic evaluations may be included for determination of disease recurrence: CT, plain films, bone scans, MRI, US, and PET.
- Response Category Evaluation (as in 5.2)

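### Section 5.4.2 specifies only a follow-up slope for TGFβ1, so no stated model uses the pre-radiotherapy or end-of-radiotherapy value that the primary objective names

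*Combined protocol and SAP*

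**What the plan says.** The third primary objective in section 1.1.1 reads "To determine if pre-treatment, post-treatment, and follow-up measurements of TGF" β1 in urine and plasma can predict late gastrointestinal toxicity. It names three kinds of measurement.

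Section 3.2.1.2.2 schedules samples before treatment, before radiotherapy if that differs, and then "at completion of radiotherapy and in follow- up at 1, 3, 6, 12, 24, and 36 months". Section 3.3.3 uses the word in the same sense: "Patients will be seen for routine follow-up at 1, 3, 6 and 12, 24, and 36 months post-radiotherapy".

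Section 5.4.2 opens broadly, with levels "at various timepoints during and after therapy are associated with late gastrointestinal toxicity". It then singles out change over time as being of particular interest, and defines that change as a per-patient slope, "evaluated by estimating a slope using least-squares regression on each patients repeated follow-up measurements", entered in a logistic regression for RTOG grade 2 or higher at 12 months. The emphasis is on the upward direction: "Interest will focus on whether a positive change in TGF" β1 goes with toxicity. The power statement assumes 76 evaluable patients and that "50% of estimated slopes are positive", and gives 93% power for "80% for a positive slope as compared with 40% for a negative or zero slope with a Chi-square test at the 0.05 significance level". A continuous version of the same slope is mentioned as likely to be more powerful.

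For the DNA markers, section 5.4.1 handles change differently. One of its analyses takes the proportion of positive markers at 3 months minus the proportion at baseline.

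**The concern.** A slope through post-radiotherapy samples describes what happens after treatment. It carries no information about the level reached by the end of radiotherapy relative to where the patient started. Two quite different patients, one raised by radiotherapy and still raised, the other never changed, therefore have the same expected predictor value. Entering the slope as continuous does not help, because the missing information is the level and its reference, not the cut-point.

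The background in section 1.2.3.2 cites both acute and chronic TGFβ overexpression in irradiated bowel, so a sustained early rise is one plausible signature of risk. If that is how the marker works, the specified analysis could report a null for a useful marker. Even if it is not, the plan collects pre-radiotherapy and end-of-radiotherapy TGFβ1 for a primary objective without saying how either enters a model.

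**Working it through.** **1. The plan's own figures.** With 38 patients per group, 80% versus 40%, two-sided 0.05 and continuity correction:

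- corrected difference = 0.40 − (1/38 + 1/38)/2 = 0.3737
- pooled SE = √(0.6 × 0.4 × 2/38) = 0.1124; × 1.96 = 0.2203
- unpooled SE = √((0.8 × 0.2 + 0.4 × 0.6)/38) = 0.1026
- power = Φ((0.3737 − 0.2203)/0.1026) = Φ(1.495) = 93.3%

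The stated 93% reproduces. Without the correction it would be 96.0%. The 95% chance of at least 76 evaluable patients also reproduces: P(X ≥ 76) for Binomial(120, 0.70) is 95.3%. The arithmetic is sound; the point concerns how the predictor is defined.

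**2. Slopes for simple profiles.** Take visits at months 1, 3, 6 and 12, up to the outcome. The mean time is 5.5, the deviations are −4.5, −2.5, 0.5 and 6.5, and their squares sum to 69. The slope is Σ(deviation × value)/69, with values as multiples of the pre-radiotherapy level.

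- Never changed (1, 1, 1, 1): 0/69 = 0.000
- Doubled and stayed (2, 2, 2, 2): 0/69 = 0.000
- Doubled, then slow decline (2.0, 1.9, 1.8, 1.6): (−9.0 − 4.75 + 0.9 + 10.4)/69 = −2.45/69 = −0.036 per month

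Adding only the end-of-radiotherapy sample leaves the second slope at zero. A pre-radiotherapy reference is needed to separate it from the first.

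**3. With assay noise.** For a pre-radiotherapy level of 100 and independent noise of SD 10, 20 or 40 (assumed), the probability of a positive follow-up slope is about 50% for the patient steady at 100 and about 50% for the patient steady at 200.

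**4. Effect on the test.** The documents give no TGFβ1 trajectories or variances, so every input here except n = 76 and 60% toxicity is an assumption. Simulated trials used a between-patient log SD of 0.5 and within-patient log SD of 0.3, 0.4 or 0.5. Toxic patients sit at 1.5 times their pre-radiotherapy level at every follow-up visit. The tests are uncorrected chi-square at 0.05 on slope sign, and on a median split of the mean log ratio (months 1, 3, 6) to the pre-radiotherapy value. Rejection rates are for SD 0.3 / 0.4 / 0.5; repeat runs agree to about two percentage points.

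| Non-toxic patients at months 1, 3, 6, 12 | Slope sign | Ratio to pre-radiotherapy |
|---|---|---|
| 1.0, 1.0, 1.0, 1.0 (back at baseline by month 1) | about 5% throughout | 97 / 83 / 66% |
| 1.5, 1.25, 1.0, 1.0 (resolve by month 6) | 85 / 63 / 47% | 48 / 29 / 21% |
| 1.5, 1.4, 1.25, 1.0 (resolve by month 12) | 90 / 72 / 52% | 12 / 9 / 8% |

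In the first row, a t-test on the continuous slope, standing in for the logistic model, rejects 4 / 5 / 5%. If the pre-radiotherapy sample (assumed 1.5 months before radiotherapy ends) and the end-of-radiotherapy sample are put into the slope, the first-row figures become 53 / 32 / 23% for the sign and 72 / 47 / 32% for the continuous slope. A straight line fits a step poorly.

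**The case against.** The strongest reply is that a trajectory measure suits the biology. Section 1.2.3.2 describes late toxicity as a process that evolves over months to years and says the kinetics of TGFβ1 tracked pneumonitis in lung patients. The second and third rows of the table bear this out: when patients without toxicity resolve during follow-up, the slope beats the ratio clearly. This stands, and it is why the slope should stay.

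A second reply is that section 5.4.2 opens with levels during as well as after therapy and does not tie the slope to named visits, so earlier samples might be intended. That is fair as far as it goes. A reader might infer that the pre-treatment part of the objective has been abandoned, and the opening sentence does not support going that far. But it states an aim without a model, and the sentence that defines the analysis says follow-up, which the protocol elsewhere keeps apart from the earlier samples.

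Third, this is a pilot with no treatment decision attached, and extra predictors add tests at an unadjusted 0.05. The multiplicity cost is real but small, and it can be handled by ranking the predictors.

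**Conclusion.** The gap is real: no specified TGFβ1 model uses a pre-radiotherapy or end-of-radiotherapy value, and the specified slope cannot tell a sustained early rise from no change. This is a worthwhile improvement to the plan, not an error in its arithmetic.

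Three stronger conclusions are tempting and should not be drawn.

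- That patients who rise and plateau are classed as low risk. An exactly zero slope needs a noise-free assay; with noise the sign is about a coin flip. The positive versus negative-or-zero split belongs to the power calculation, and the plan does not call either group low risk.
- That the planned test has no power. The 5% figure assumes the groups are fully separated by month 1; under the two resolving profiles the same test rejects 47% to 90% of the time.
- That the slope finds only a steady rise. It also separates persistence from resolution during follow-up.

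The documents do not show which trajectory is likely, so no single power loss can be quoted. What can be said is that each predictor is weak where the other is strong.

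**What to change.** In section 5.4.2:

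- Keep the slope and the 93% power statement attached to it, and state which visits enter the slope.
- Add one baseline-referenced predictor of 12-month RTOG grade 2 or higher, separately for plasma and urine: the mean over the early follow-up visits (for example months 1, 3 and 6) of the log ratio of TGFβ1 to the patient's own pre-radiotherapy value.
- Report the log ratio of the end-of-radiotherapy value to the pre-radiotherapy value as supportive.
- Say which predictor is primary, or apply a simple adjustment. Slope and mean ratio in two fluids make four tests, so Bonferroni would use 0.05/4 = 0.0125 for each. Naming the slope as primary leaves its power statement at 0.05 as written; splitting alpha would require recalculating it.

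The change is to analysis wording only, since every sample is already scheduled. The costs are one or two more predictors per fluid to report, and the loss from the ratio analysis of patients who have no pre-radiotherapy sample. It should be written in before the TGFβ1 results are linked to toxicity.

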Protocol 07C0111

IRB approval date 2/11/2007

**A Pilot Study of Markers of Tumor Burden and Radiation Toxicity in
the Blood, Urine, and Stool of Patients Receiving Radiotherapy for
Gastrointestinal Malignancies**

Principal Investigator: [name].¹

Study Chairperson: [name].²

Associate Investigators: [name].¹
[name], MS¹
[name], RN³
[name], RN³
[name], RN¹
[name].²
[name].²
[name].²
[name], PhD⁵
[name].⁴
[name].⁶
[name].⁶
[name], B.S., CRTP⁷
✓ [name].⁸
[name], MD⁴
[name], MD⁴

¹Radiation Oncology Branch, CCR, NCI
[name]
[name]
[name]
[contact]
[contact]

²Surgery Branch, Center for Cancer Research, NCI

³Department of Nursing and Patient Care Services, CC, NIH

⁴Medical Oncology Branch, CCR, NCI

⁵Cancer Therapeutics Branch, CCR, NCI, NIH

⁶Department of Diagnostic Radiology, CC, NIH

⁷Clinical Research Training Program, Office of the Director, NIH

⁸Laboratory of Pathology, CCR, NCI, NIH

PRECIS

Background:

- Gastrointestinal (GI) carcinomas represent one of the most commonly diagnosed malignancies in the United States¹.
- A sensitive and specific marker of tumor persistence or recurrence would permit a more accurate determination of the appropriateness of adjuvant therapy in patients with no clinical evidence of disease following curative resection and allow the diagnosis of recurrences at earlier stages that may be amenable to curative salvage therapies.
- A biomarker detectable shortly after treatment or in the early stages of chronic radiation toxicity may allow the identification of patients at risk and early intervention.

Objectives:

- Our primary objective is to determine if patient specific tumor markers in stool, urine, or serum can be reliably detected prior to treatment and followed after treatment to monitor the extent of residual disease.
- A second objective is to evaluate the predictive value of potential markers of chronic gastrointestinal injury after radiotherapy.

Eligibility

- Age \geq 18 years
- Histologically confirmed carcinoma of the gastrointestinal tract (esophagus, stomach, pancreas, rectum)
- Planned to receive radiotherapy to the site of the gastrointestinal malignancy on an NCI protocol

Design:

- This protocol provides a means of acquiring tissue, serum, urine, and stool samples from patients who will receive radiation therapy as part of their treatment for gastrointestinal malignancies.

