1.2.3.2 Markers of radiation-induced gastrointestinal toxicity in serum, plasma, urine, and stool

While clinical markers provide a measure of acute and chronic radiation toxicity, there is little ability to predict which patients may eventually experience chronic radiation toxicity. The ability to identify patients shortly after treatment destined to experience radiation toxicity may eventually allow early intervention. As the biologic events responsible for chronic radiation toxicity have become better understood, it has become clear that chronic radiation toxicity is a dynamic process that develops over the course of months to years after treatment. Many key processes in this ongoing injury are being defined, and agents are being developed with the intent of mitigating ongoing damage. Development of a biomarker that could accurately predict the likelihood of eventual radiation toxicity would allow selection of patients at high risk of toxicity for trials of these agents and provide candidate biomarkers of response to preventative therapy.

Several mechanisms of this ongoing injury in normal tissues have been described from evaluation of preclinical models. Depletion of stem cells in the bowel wall with resulting denudation has been implicated in acute intestinal injury, and it was long thought that late radiation toxicity of the bowel was a result of progressive damage as a consequence of this stem cell depletion³⁴. Recently, inflammatory cytokines have been implicated in bowel and other tissues as possible mediators of chronic inflammation and fibrosis following radiation³⁶. In addition, the expression of numerous collagens and matrix remodeling peptides have been shown to be altered early in preclinical models of late GI injury³⁷⁻³⁹ and in the affected tissues of patients with late GI radiation toxicity⁴⁰. It is possible that early detection of this ongoing inflammation and pro-fibrotic pathways may eventually allow early intervention to mitigate late toxicity.

Table 1: Candidate markers of toxicity to be evaluated on this protocol

Plasma	Serum	Urine	Stool
TGFβ1	Neutrophil elastase	TGFβ1	Neutrophil elastase
	Procollagen peptides	Procollagen peptides	Calprotectin
		Intestinal permeability	pH

- TGF β 1

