5.4 Statistical Section

The two primary objectives are to (i) to examine whether tumor-specific DNA mutations and aberrant DNA methylation at the time of diagnosis and during follow-up is associated with disease persistence, recurrence, or survival, and (ii) whether changes in TGF β 1 in the urine and plasma is associated with late gastrointestinal toxicity. We will discuss analysis and sample size considerations for each primary objective in turn.

5.4.1 Association between tumor-specific DNA markers and subsequent disease.

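### The TGFβ1 objective is worded as prediction, but section 5.4.2 plans only an association test, with no accuracy estimates or intervals and no time limit on the slope

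*Combined protocol and SAP*

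**What the plan says.** Section 1.1.1 lists as a primary objective whether serial TGFβ1 measurements "in the urine and plasma can be used to predict late gastrointestinal toxicity". The precis likewise aims to "evaluate the predictive value of potential markers of chronic gastrointestinal injury after radiotherapy". Section 1.2.3.2 gives the reason for wanting such a marker: it "would allow selection of patients at high risk of toxicity for trials of these agents".

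The opening of section 5.4 words the same objective differently, as whether changes in TGFβ1 "in the urine and plasma is associated with late gastrointestinal toxicity". Section 5.4.2 follows that wording. Change in TGFβ1 is "evaluated by estimating a slope using least-squares regression on each patients repeated follow-up measurements", and the slope is related to RTOG grade ≥2 at 12 months by logistic regression, with and without adjustment for dosimetry. Interest centres on whether a positive change "over time (positive slope) is associated with an RTOG" grade ≥2 toxicity. The sample size argument is a Chi-square test of 80% against 40% toxicity, with 76 evaluable patients and half of the slopes positive. The stated power is 93%.

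For TGFβ1 the section names no sensitivity, specificity, AUC, confidence interval or validation. Section 5.4.3 does plan sensitivities and specificities, but only for the DNA tests against tumor biopsy. Sections 3.1.1 and 3.2.1.2.2 schedule blood and urine samples up to 36 months, and 5.4.2 does not say which of them enter the slope.

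**The concern.** Association and prediction are different questions. An odds ratio can be clearly different from 1 while the marker separates patients only moderately. If the trial ends with a significant logistic coefficient, it has answered the question in 5.4. The question in 1.1.1 stays open unless someone also reports how often the marker is right, and with what precision. Measures or cut-points chosen after the data are seen would be post hoc.

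Timing matters as well. The outcome is assessed at 12 months, but the follow-up samples include those at 12, 24 and 36 months. A slope that uses a value taken at or after the outcome visit describes something concurrent with the toxicity, or following it. Any accuracy figure computed from such a slope would not measure prediction.

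**Working it through.** **Inputs, all from 5.4.2.** 76 evaluable patients; 50% positive slopes, so 38 and 38; toxicity 80% with a positive slope and 40% otherwise; about 60% overall; Chi-square test at 0.05.

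**The plan's own figures.**
- Base rate: 0.5×0.80 + 0.5×0.40 = 0.60, which agrees with the stated 60%.
- Evaluable number: P(76 or more of 120) at a rate of 0.70 is 95.3%, which agrees with the stated 95%.
- Power, by exact enumeration with 38 per group: 92.9% for the continuity-corrected Chi-square and 95.8% without correction. The stated 93% reproduces with the correction.

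**Accuracy of the slope-sign cut at the design point.**
- PPV = 80% and NPV = 1 − 0.40 = 60%. These come directly from the two compared proportions.
- Sensitivity = 0.5×0.80/0.60 = 66.7%.
- Specificity = 0.5×0.60/0.40 = 75%.
- Odds ratio = (0.80/0.20)/(0.40/0.60) = 6. AUC of the two-level rule = (0.667 + 0.75)/2 = 0.71.

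**Precision with 76 patients.** Whole-number counts nearest the design point, with exact (Clopper-Pearson) 95% intervals. The denominators differ slightly because 80% and 40% of 38 are not whole numbers.

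| Measure | Count | Estimate | 95% CI |
|---|---|---|---|
| PPV | 30/38 | 79% | 63–90% |
| NPV | 23/38 | 61% | 43–76% |
| Sensitivity | 31/46 | 67% | 52–80% |
| Specificity | 23/31 | 74% | 55–88% |

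Pairing 30/38 with 15/38 (45 events) gives sensitivity 30/45 = 67%, with interval 51–80%, which is essentially the same.

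**A just-significant result.** Take 46 events, since 0.60×76 = 45.6. A split of 27 versus 19 gives p = 0.060 without correction. A split of 28 versus 18 gives p = 0.019 uncorrected and 0.035 corrected, so it is the smallest significant split in the expected direction. Its accuracy is:
- PPV 28/38 = 74%
- NPV 20/38 = 53%
- sensitivity 28/46 = 61%
- specificity 20/30 = 67%

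**Timing.** Follow-up samples are due at 1, 3, 6, 12, 24 and 36 months. Only those at 1, 3 and 6 months are sure to precede the 12-month toxicity assessment.

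**The case against.** The strongest reply is that the plan is nearer to prediction than it looks. The powered comparison is of toxicity rates given slope sign, and those rates are the PPV and 1−NPV. The same two-by-two table yields sensitivity and specificity, and the logistic model yields fitted risks. This stands: what is missing is a commitment to report accuracy with intervals, and any assessment of the fitted risks.

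It is also a pilot study of candidate markers, and section 5.4 openly words its objective as association. Testing association first is defensible. That answers 5.4, but 1.1.1 is listed as primary and still says *predict*.

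Several stronger readings are tempting, and the documents do not support them.
- *Forty percent of patients called low-risk would still have toxicity.* The plan defines no low-risk group. The sign split serves the power calculation and the stated focus of interest, while the logistic analysis can treat the slope as continuous. The 40% is a planning assumption.
- *The marker would be too weak for its stated use.* Section 1.2.3.2 wants to select patients at high risk for trials, so PPV is the relevant figure. At the design point it is 80% against a 60% base rate, which may be useful. That cannot be judged without the PPV and its interval.
- *The objective would be declared met on a p-value.* Section 5.4 states no such success rule.

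**Conclusion.** The point holds as a mismatch between objective and analysis. It is not a power error: the 93% reproduces. As written, a significant result would support association and leave open how well TGFβ1 predicts. The gap is material because significance is compatible with quite different performance: PPV from about 74% and NPV from about 53% at the edge of significance, against 80% and 60% at the design point. With 38 patients per slope group, the 95% intervals for PPV and NPV are roughly 27 and 33 percentage points wide.

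These figures assume the plan's 76 evaluable patients, equal slope groups and 60% toxicity, and they describe the cut at zero only. A different split or base rate would change them. The undefined sampling window does not depend on these assumptions, and it has to be settled before any accuracy figure can be read as prediction.

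**What to change.** In section 5.4.2:
1. Keep the association test.
2. Compute each patient's slope only from samples taken before the 12-month toxicity assessment, and list the visits that count.
3. For slope >0 versus ≤0, in plasma and in urine, report PPV, NPV, sensitivity and specificity with exact 95% intervals. Show PPV beside the observed overall toxicity rate.
4. For the continuous slope, report an internally validated AUC with a confidence interval.
5. State that any conclusion about prediction rests on these estimates, and that otherwise only association will be concluded. Reconcile the wording of 1.1.1 and the precis with 5.4 accordingly.

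The cost is a few lines of text and a little more analysis of data already being collected, with no extra patients or samples. There are two downsides. Each slope rests on fewer measurements and so is noisier, and a significant odds ratio on its own no longer supports the word *predict*.
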